In general the evidence in aBME is limited. A few prospective studies has been conducted, and only one larger RCT. This RCT included 635 participants, where aBME was performed from week 36 of pregnancy. They were not able to detect any difference in gestational age at birth or report any adverse events in relation to the aBME. Before the larger RCT they conducted a pilot study, which consisted of 43 participants. Our aim with this study is to primarily test safety and feasibility with the procedure aBME from week 34, and since no study has been done from this week of pregnancy, a reliable power calculation is not possible to make. Therefore we estimated that 30 participants in each group is a realistic and feasible number to include in the pilot study. To detect a difference in gestational age at birth based on 80% power, we estimated that we would need a total of 176 participants, 88 in each group (mean, SD, derived from Soltani et al(19)). If the pilot study shows no trend towards a higher proportion of preterm birth in the intervention group, we will proceed to the larger trial.

Data collection:

Demographic data on the mothers (maternal age, education level, ethnic background, parity and smoking status) will be obtained through medical files. Infant data on gestational age, complications such as preterm contractions or birth and feedings from birth, will be obtained from medical records after birth. To obtain data on aBME and breastfeeding rates after birth, we will use SMS tracking via an app based in the RedCap system. From intervention start until 8 weeks after birth participants in the intervention group will receive a weekly sms, with questions on how many times they stimulated and if they were capable of expressing any milk. The control group will receive a weekly message which regards if they have been giving birth, to be able to initiate the questions on breastfeeding. After birth questions will regard breastfeeding initiation. After eight weeks the mothers experience and evaluation on the study will be evaluated in an online questionnaire.

Data analysis and statistics:

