Data will be collected in order to meet the CONSORT guidelines for Randomized Controlled Trials. Comparability of the two groups by intention to treat analysis. Where data are normally distributed, comparison of means will be done using unpaired t-tests. If data are not normally distributed a non-parametric test for unpaired data will be used, eg. Mann-Whitney test or permutation test. Multivariate

analysis will be carried out, if data shows differences in maternal or infant characteristics possibly affecting outcome.

[Interruption of the trial](#)

The involved investigators can stop the trial if the protocol is not followed or unexpected adverse effects in relation to the aBME such as contractions, vaginal bleeding or overrepresentation of preterm birth in the intervention group. The investigators in charge can pull out participants if they find it irresponsible to continue due to side effects or new pregnancy related conditions, where aBME could be contraindicated. Participants can at any time retract their consent and stop the intervention.

[Patient insurance](#)

This trial is covered by the Patient Compensation Scheme and Labour Market Insurance.

[Publication](#)

All results, positive, negative as well as inconclusive results will be published.

[Possible clinical implication:](#)

We expect this initiative to have positive impact on both mother and infant with improved breastfeeding rates and mothers confidence with breastfeeding. If aBME from 34 weeks does not induce preterm birth, we aim to investigate if this procedure is safe earlier in pregnancy and especially among pregnant women at increased risk of preterm delivery. In the long term, this could increase the number of preterm infants fed exclusively MOM and possibly contribute to improved gut health and neurodevelopmental outcome for preterm infants.

Referencer

1. WHO/UNICEF. Global nutrition targets 2025: breastfeeding policy brief (WHO/NMH/NHD/14.7). Geneva: World Health Organization; 2014.

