### 2.2 Adherence to the intervention

We consider all participants who answer weekly questionnaires until 8 weeks post-partum as full completers. E.g. if participants try to follow the intervention as well as possible, but do not stimulate the breast the recommended fourteen times a week, we will still consider them as completers of the study, if they have stayed in the study during the intervention and until eight weeks after birth. However, we will differentiate between study completion and intervention completion. Intervention completion is defined as participants who follow the intervention as well as possible until birth but do not answer all eight questionnaires. These participants will be included in the analysis for gestational age at birth, but will only be included in the breastfeeding analysis as long as they have answered the weekly questions. If participants do not want to perform stimulation anymore, we consider this as a withdrawal of consent. If participants are not adherent to the randomized group, e.g. they start to stimulate antenatal even though they are in the control group, we consider them as excluded from the study.

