### 2.3 Intention to treat (ITT) and per protocol (PP) analysis

We will apply a modified ITT principle, considering only the participants who started the antenatal stimulation and/or participated in the breastfeeding consultation and as the ITT population. Participants who drop out before the breastfeeding consultation for any reason will not be included in any of our analyses. We consider PP as all of the participants who completed questionnaires until 8 weeks post-partum, no matter how well they complied with the intervention. We will apply ITT and PP analysis to our primary and secondary outcomes.

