### 3.4 Withdrawal/dropout from the study

We will register the reason for withdrawal. We will divide withdrawal into the following categories:

1. Withdraw because of investigations in relation to the trial
2. Withdraw because of side effects in relation to the intervention
3. Withdraw because of time consumption in relation to the trial
4. Withdraw because of other reasons (will be described)
5. The participant is excluded from the trial because it is in the participant's best interest
6. The participant is excluded from the trial because the participant does not want to follow the instructions related to the randomization group
7. The participant is excluded from the trial due to loss of contact
8. The participant is excluded from the trial due to other reasons (will be described)

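### The plan does not separate stopping antenatal expression from leaving the trial, so it is unclear whether group A women taken off for safety reasons stay in the gestational-age comparison

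*Protocol*

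**What the plan says.** - **Protocol, Interruption of the trial:** "The investigators in charge can pull out participants if they find it irresponsible to continue due to side effects or new pregnancy related conditions". The sentence goes on to limit those conditions to ones in which aBME might be contraindicated. Under Trial design, allocation is open to participants and to the investigators analysing the data.
- **SAP 3.4, category 5:** "The participant is excluded from the trial because it is in the participant's best interest". The section is introduced as a register of reasons for withdrawal.
- **SAP 2.2** describes two classes. Study completers qualify "if they have stayed in the study during the intervention and until eight weeks after birth". Intervention completers are "participants who follow the intervention as well as possible until birth but do not answer all eight questionnaires", and this section states explicitly that they enter the gestational-age analysis. It says nothing about women whose aBME an investigator has stopped.
- **SAP 2.3** defines modified ITT by "considering only the participants who started the antenatal stimulation and/or participated in the breastfeeding consultation", drops from all analyses only those who leave before the consultation, and applies ITT and per-protocol (PP) analysis to the primary and secondary outcomes. PP requires questionnaires up to 8 weeks, "no matter how well they complied with the intervention".
- **Protocol, Data analysis and statistics:** "Comparability of the two groups by intention to treat analysis".
- **Protocol, Data collection:** gestational age and related infant data "will be obtained from medical records after birth", with no exception for removed women.
- **Protocol, Sample Size:** the larger trial follows if the pilot shows no trend to more preterm birth in group A.
- **SAP 4.5:** no imputation; available data only.

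**The concern.** Both parts of the trigger, side effects and new conditions that contraindicate aBME, concern an activity that only group A is meant to perform. The protocol itself gives contractions and vaginal bleeding as examples of possible adverse effects, and these are plausible forerunners of early birth. Removal could therefore be related to the primary safety outcome, occur mainly in one arm, and be decided by people who know the allocation.

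That does no harm if removal only ends expression. If it ends participation and the birth is no longer counted, group A may lose births that are earlier than average. Nothing replaces them, because missing data are not imputed. Both the gestational-age comparison and the preterm proportion behind the decision to proceed would then lean towards finding aBME safe. Neither document says whether modified ITT or PP supplies that proportion.

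**Working it through.** **1. Where does a removed woman fall?** Take a woman randomised to A who attends the week 33 consultation, starts aBME at 34+0, and is taken off it by an investigator before birth.

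| Text | Her status |
|---|---|
| SAP 2.3, modified ITT | In: she attended the consultation and started stimulation |
| Protocol, ITT statement | In |
| Protocol, records as source | Gestational age obtainable without her further effort |
| SAP 2.2, study completer | Out if removal means she has not stayed in the study |
| SAP 2.2, intervention completer | Out: she did not follow the intervention until birth |
| SAP 3.4, category 5 | Logged as excluded; use of her data not addressed |
| SAP 2.3, PP | In if she goes on answering questionnaires, out if she stops |

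No sentence says whether her record is still used after removal.

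**2. The plan's own figure.** The pilot's 30 per arm was set on feasibility. The 88 per group for a larger trial cannot be reproduced, because the mean and SD are not given. Solved backwards at two-sided 0.05 (sidedness assumed) and 80% power, d = (1.960 + 0.842) × √(2/88) = 0.422 SD.

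**3. Effect on the decision to proceed, if removed births are lost.** All risks and loss rates here are assumptions, since the documents give none. Let pA and pB be the true preterm risks, and let rp and rt be the chances that a preterm or term birth in A is lost. With n = 30 per arm, *no trend* is taken to mean that A's observed proportion is not above B's.

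Expected observed risk in A = pA(1−rp) / [pA(1−rp) + (1−pA)(1−rt)]. For pA = 0.10, rp = 0.25, rt = 0, this is 0.075/0.975 = 7.7%.

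Exact enumeration, 10% v 5%:

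| rp | Observed A risk, rt = 0 | P(no trend), rt = 0 | Observed A risk, rt = 5% | P(no trend), rt = 5% |
|---|---|---|---|---|
| 0 | 10.0% | 0.312 | – | – |
| 10% | 9.1% | 0.320 | 9.5% | 0.229 |
| 25% | 7.7% | 0.352 | 8.1% | 0.288 |
| 50% | 5.3% | 0.466 | 5.5% | 0.433 |

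With rt = 0, 15% v 5% goes from 0.133 to 0.139, 0.167 and 0.284; 8% v 4% goes from 0.354 to 0.365, 0.397 and 0.504. Two entries with term losses lie below the no-loss 0.312. Unequal denominators break ties, and a tie would have counted as no trend. The expected observed risk in A still falls below 10% in all six loss cases.

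In counts: an assumed 3/30 (10.0%) v 1/30 (3.3%) becomes 1/28 (3.6%) v 3.3% if two preterm cases in A are dropped.

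**4. Effect on the rank-sum test.** This is the worst case, in which the lost births are A's shortest gestations. It uses simulation with normal gestational age.
- At the back-solved 0.42 SD (assumed SD 10 days, true shortening 4.2 days), the chance of a significant harm finding is 34% with no loss and 29%, 22% or 17% with 1, 2 or 3 births lost. The mean difference shrinks to −3.6, −2.9 and −2.3 days.
- At an assumed 1-week shortening with SD 1.6 weeks (1/1.6 = 0.63 SD), it is 0.64 with no loss and 0.58 or 0.51 with 1 or 2 births lost. If the losses are random it is 0.63 for either number.

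The damage comes from selective loss; the smaller sample alone costs little.

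**The case against.** The strongest reply is that SAP 3.4 is a list of reason codes and defines no analysis set. SAP 2.3 does define one. It keeps any woman who reached the consultation, removes only earlier dropouts, and applies ITT to the primary outcome. Gestational age comes from records, and removals are logged, so they can be counted. Investigators may also halt the trial if preterm birth is overrepresented in group A. Discretion to stop aBME is necessary, and an untreated control arm always makes such a trigger one-sided.

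Most of this stands. A reader might infer that the SAP flatly contradicts its own modified ITT set, or that intervention completers are the only women with a stated place in the gestational-age analysis. The documents support neither: SAP 2.3 covers the whole modified ITT set for the primary outcome, and SAP 2.2 reads more as a rule for incomplete questionnaires than as an exhaustive inclusion list.

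The reply does not remove the ambiguity. SAP 2.2 treats no longer wanting to stimulate as withdrawal of consent and counts controls who stimulate as excluded from the study, so the SAP does elsewhere merge stopping or changing treatment with leaving the trial. The trial-level stop also depends on preterm births being counted. The size objection is fair too. At 10% risk about 3 of 30 births in A are preterm, so losses of 10%, 25% and 50% amount to 0.3, 0.75 and 1.5 women.

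**Conclusion.** The point holds as an unresolved inconsistency, minor to moderate. The better reading, through SAP 2.3 and the use of records, keeps removed women and gives zero bias from this source. The literal reading of the removal wording and SAP 2.2 would lose births selectively from group A and lean the safety comparison towards no harm.

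The size under the literal reading is unknown. No removal rate is documented, the women are low-risk, and every preterm risk, SD and shift used above, apart from the back-solved 0.42 SD, is an assumption. A reader might also infer that any loss makes a decision to proceed more likely. The enumeration does not show that for small losses, because ties are broken when term births are lost as well. The participant information (Appendix 1) is not in the supplied text and might settle what happens to data after removal.

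**What to change.** - In Interruption of the trial and SAP 3.4 category 5, replace removal with *stops aBME; remains in the trial*. Leave the clinical judgement on when to stop unchanged.
- In SAP 2.2, state that all women in the modified ITT set, including those whose aBME was stopped, are analysed in their randomised group for gestational age and preterm birth. Take both from medical records unless consent for record use is withdrawn.
- Apply the same rule to the SAP 2.2 sentences on women who no longer want to stimulate and on controls who stimulate, and to SAP 3.4 category 6 (not following group instructions).
- In SAP 2.3, name modified ITT as the basis for the decision on the larger trial, with PP as supportive.
- Report investigator removals by arm.

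The cost is wording: one protocol paragraph, two SAP 3.4 categories, and a few sentences in SAP 2.2 and 2.3. Gestational age already comes from records, so no visits are added. If this is already the intention, the edit simply records it.

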## Table of contents

### 1. List of Abbreviations

aBME: Antenatal breastmilk expression

GA: Gestational age

MOM: Mother's own milk

DHM: Donor human milk

## 2. Statistical Principles

### 2.1 P values and confidence intervals

We will consider a P value of < 0.05 as statistically significant with a significant level at 95%.

### 2.2 Adherence to the intervention

We consider all participants who answer weekly questionnaires until 8 weeks post-partum as full completers. E.g. if participants try to follow the intervention as well as possible, but do not stimulate the breast the recommended fourteen times a week, we will still consider them as completers of the study, if they have stayed in the study during the intervention and until eight weeks after birth. However, we will differentiate between study completion and intervention completion. Intervention completion is defined as participants who follow the intervention as well as possible until birth but do not answer all eight questionnaires. These participants will be included in the analysis for gestational age at birth, but will only be included in the breastfeeding analysis as long as they have answered the weekly questions. If participants do not want to perform stimulation anymore, we consider this as a withdrawal of consent. If participants are not adherent to the randomized group, e.g. they start to stimulate antenatal even though they are in the control group, we consider them as excluded from the study.

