## 3. Study design

### 3.1 Randomization

All participants will be randomized 1:1 into one of two arms: Group A aBME from week 34+0 or Group B no aBME. Randomization in this pilot trial will not be blinded to participants or investigators performing the data analysis due to the intervention type.

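### The SAP contradicts itself on whether women who stop expressing, and control women who start, stay in the gestational-age analysis, although the protocol states intention to treat

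*SAP*

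**What the plan says.** The protocol (Data analysis and statistics) says that the groups will be compared by intention to treat, with no modification.

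SAP 2.2 sets rules for two kinds of non-adherence:

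- Women in the antenatal expression (aBME) arm who stop: "If participants do not want to perform stimulation anymore, we consider this as a withdrawal of consent".
- Control women who cross over: if "they start to stimulate antenatal even though they are in the control group, we consider them as excluded from the study". SAP 3.4, category 6, has the same idea: "The participant is excluded from the trial because the participant does not want to follow the instructions related to the randomization group".

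SAP 2.2 has one sentence about who is kept for the primary outcome: "These participants will be included in the analysis for gestational age at birth". It refers to women who carry on with the intervention until birth but do not return every questionnaire.

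SAP 2.3 defines the sets without regard to adherence. The modified intention-to-treat population is formed by "considering only the participants who started the antenatal stimulation and/or participated in the breastfeeding consultation". The per-protocol set is everyone who completed the questionnaires to eight weeks, "no matter how well they complied with the intervention". Both sets are applied to the primary outcome. The only exclusion stated in 2.3 is: "Participants who drop out before the breastfeeding consultation for any reason will not be included in any of our analyses".

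SAP 4.5 adds that nothing is imputed and that available data are used.

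**The concern.** Gestational age at birth is the primary safety outcome, and under the protocol's Sample Size section the larger trial goes ahead if the pilot shows no trend to more preterm birth in the aBME arm. Who is counted therefore bears on both the safety result and the decision to proceed.

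The stopping rule can act only in the aBME arm, since only those women have stimulation to stop. Contractions, bleeding or pain could prompt both stopping and an early birth, and SAP 3.4 lists side effects as a reason for withdrawal. Removing such women selects on behaviour after randomisation that may be related to the outcome. The trial is also open: it "will not be blinded to participants or investigators performing the data analysis due to the intervention type". An unsettled analysis set would then be settled by people who can see allocation and outcome.

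None of this is forced by the data source. The protocol (Data collection) takes gestational age from medical records after birth, so it depends on neither adherence nor questionnaires.

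**Working it through.** **1. The passages side by side.** The protocol (Intervention) gives the consultation to all women in both arms in week 33, before stimulation starts at 34+0. Women who reach either 2.2 rule will therefore normally have attended it.

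| Woman | SAP 2.2 / 3.4 | SAP 2.3 modified ITT | SAP 2.3 per protocol | Protocol |
|---|---|---|---|---|
| Control who stimulates | Excluded from the study | In, if she attended | In, if questionnaires complete | In |
| aBME woman who stops | Treated as consent withdrawn | In | In, if questionnaires complete | In |
| aBME woman who leaves or is taken out for side effects | Category listed; use of later records not stated | In | In, if questionnaires complete | In |
| Leaves before the consultation | – | Out | Out | In |

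The first row is a direct contradiction. The second is a strong implication: 2.2 does not literally say that a stopper's gestational age is omitted. But the outcome arises after the deemed withdrawal, the 2.2 sentence on retention covers only women who continue to birth, and no passage says that 2.3 overrides 2.2. The last row is a lesser departure from the protocol; it acts in both arms and its direction is unknown.

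**2. Power is not the issue.** The protocol's 88 per arm cannot be reproduced forward, because the mean and SD are not given. Inverting it (two-sided 0.05, 80% power, normal approximation) gives a standardised difference of (1.960 + 0.842) × √(2/88) = 0.422. Power is Φ(0.422/√(1/n₁ + 1/n₂) − 1.960): 37% at 30 v 30 and 34% at 24 v 30. The question is selective removal.

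**3. Counts (assumed; the documents give no rates).** Difference in preterm proportion, aBME minus control:

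- All women: 4/30 − 1/30 = 10.0 points
- One, two or three preterm stoppers dropped: 3/29 − 1/30 = 7.0; 2/28 − 1/30 = 3.8; 1/27 − 1/30 = 0.4
- Six term stoppers dropped: 4/24 − 1/30 = 13.3
- One stimulating control with a preterm birth excluded: 4/30 − 0/29 = 13.3

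**4. Chance of seeing no trend.** The documents do not define this; it is read here as an aBME preterm proportion no higher than control. With 30 per arm, control risk 5% and no control exclusions, let p be the true aBME risk, and s₁ and s₀ the shares of preterm and term aBME women dropped. Each aBME woman is kept-preterm with probability p(1 − s₁), kept-term with probability (1 − p)(1 − s₀), and otherwise dropped. Exact enumeration at p = 15%:

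| s₁ / s₀ | Expected aBME rate among those kept | Strictly lower | Tie | No higher |
|---|---|---|---|---|
| 0 / 0 | 15.0% | 5.8% | 7.6% | 13.3% |
| 25% / 5% | 12.2% | 12.3% | 1.5% | 13.8% |
| 25% / 25% | 15.0% | 10.9% | 0.9% | 11.9% |
| 50% / 0 | 8.1% | 24.7% | 3.8% | 28.4% |
| 50% / 10% | 8.9% | 24.5% | 2.2% | 26.7% |
| 50% / 25% | 10.5% | 22.5% | 2.7% | 25.2% |

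The expected rate is p(1 − s₁)/[p(1 − s₁) + (1 − p)(1 − s₀)]; for 25%/5% this is 0.1125/(0.1125 + 0.8075) = 12.2%.

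For other true risks, the chance of no higher with all women, with 25%/5% dropped, and with 50%/0–25% dropped is:

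- 10%: 31.2%, 28.8% and 41.4–46.6%
- 20%: 5.0%, 6.3% and 14.6–17.1%

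**5. The planned rank-sum test (simulated).** There were 6,000 trials per scenario, with Monte Carlo SE at most 0.45 points. Assumptions: risks 15% and 5%; term births normal, mean 280 and SD 9 days, truncated to 259–294 days, the same in both arms; preterm births uniform on 238–258 days. Two-sided P < 0.05 with earlier aBME birth, and mean difference:

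| s₁ / s₀ | Significant | Mean difference (days) |
|---|---|---|
| 0 / 0 | 9.1% | −3.0 |
| 25% / 5% | 6.8% | −2.2 |
| 50% / 0 | 4.1% | −1.0 |
| 50% / 10% | 4.3% | −1.2 |
| 50% / 25% | 5.2% | −1.6 |
| 0 / 25% | 13.7% | −4.2 |

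**The case against.** The best defence is that 2.2 concerns adherence and 2.3 defines the analysis sets, so 2.3 governs; by naming a single exclusion, 2.3 implies that later leavers stay in. On that reading aBME stoppers are an ambiguity, and one sentence would cure it. This is a possible reading, but nothing in the SAP says so, and it leaves the explicit exclusion of controls unexplained. It is also fair that the per-protocol wording on compliance may have been meant for women who stimulate fewer than fourteen times a week, not for women deemed to have withdrawn.

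On size, every rate is assumed. Mild selection barely changes the chance of no higher (13.3% to 13.8% at 15% risk) and lowers it slightly at 10% risk. The rise in the strictly-lower column under mild selection depends partly on unequal arm sizes making ties rarer, as the unbiased 25%/25% row shows. A large effect needs about half of the preterm aBME women to stop and then deliver before term; removing women who stop and deliver at term makes the intervention look worse. The rank-sum test is weak in every scenario, and the planned Bayesian non-inferiority plot was not evaluated. All of this limits the likely size. It does not decide which women are analysed.

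Finally, whether records may be used after a woman stops depends on consent terms that are not in the documents reviewed. That stands, and the fix is conditional on it.

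**Conclusion.** The concern holds. The SAP gives two incompatible answers for control women who stimulate and, by strong implication, for aBME women who stop; the protocol's intention to treat is met only if both are kept. Applying 2.2 as written would remove randomised women for what they did after randomisation, in an open-label safety comparison that decides whether a larger trial follows.

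The size cannot be known beforehand. With 30 women per arm and few preterm births, the status of one to three women can move the observed difference by up to about 10 points in the assumed example. Strongly selective stopping roughly doubles the chance of missing a 15% v 5% excess; mild selection hardly alters it, and non-selective stopping does not bias the rate. The direction can favour or disfavour the intervention. These figures rest on assumed risks, assumed stopping patterns and the stated reading of no trend; the contradiction itself rests on the text alone. It should be resolved before the data are analysed.

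**What to change.** Amend SAP 2.2 and 2.3, and align 3.4 and 4.5, as follows:

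1. Make the primary analysis of gestational age at birth and preterm birth include all randomised women in their allocated arm, using medical records wherever consent to data use has not been withdrawn.
2. Record a woman who stops stimulating as having discontinued the intervention while remaining in follow-up, and record withdrawal of consent to data use separately. Say explicitly how women who leave or are taken out because of side effects are handled.
3. Analyse control women who stimulate in the control arm.
4. Keep the modified intention-to-treat and per-protocol sets as sensitivity analyses, state exactly who is in each, and report exclusions by arm and reason.

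The cost is SAP wording and some additional record look-ups, subject to the consent terms. The downside is some dilution from non-adherence in the primary analysis; the sensitivity sets, once clearly defined, can be read beside it. None of this changes how any woman is managed during the trial.

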A couple of studies also included in the review by Foudil-Bey et al, evaluated feedback from the women with regard to perception and experience with aBME. The negatives aspects were among others discomfort or pain during aBME, time or energy burden, anxiety about having insufficient colostrum supply and feeling of internal pressure to succeed. On the other hand, they reported a sense of ownership and confidence with breastfeeding after performing aBME. They had positive feelings about having done something for the

baby and had a feeling of preparedness by having collected colostrum ready for the first feed to the infant (12, 16-18).

On this background we hypothesize that antenatal breastmilk expression

- 1) is a safe procedure before week 36 of pregnancy
- 2) can ensure sufficient supply of MOM for the preterm infants immediately after birth
- 3) promotes feeding with exclusively MOM for preterm infants
- 4) has a positive effect on the mothers feeling of confidence and preparedness for breastfeeding

Objective

In this pilot study, we want to investigate if aBME from week 34 of pregnancy is a safe and feasible procedure for the mother and fetus. Furthermore as secondary outcomes, we want to evaluate breastfeeding rates and mother's experiences with aBME. The evaluation of the mothers experience with aBME will be a separate study conducting qualitative methods.

Methods:

Intervention

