#### Antenatal breastmilk expression

- a)** Number of weekly expressions in the intervention group, measured through weekly push messages. Reported as median and IQR, and illustrated by a barplot figure over the number of weekly expression pr. women.
- b)** Amount of breastmilk expressed if any. How many women will be capable of expressing any milk before birth in the intervention group (counts and percentages), and how many mL (median and IQR). Volume is measured by each woman using a container with an mL scale and reported through weekly self-reported push messages. Milk volumes will be illustrated by a scatterplot over milliliter pr. week compared to the week of gestation.

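### Feasibility is a primary aim, but women who stop expressing are treated as withdrawn, so the only named adherence outcome barely registers stopping

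*SAP*

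**What the plan says.** Feasibility is not a side issue. The protocol's Objective reads "we want to investigate if aBME from week 34 of pregnancy is a safe and feasible procedure for the mother and fetus", and its Sample Size section repeats "Our aim with this study is to primarily test safety and feasibility with the procedure aBME from week 34".

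SAP section 2.2 separates two kinds of non-adherence. Women who carry on at a lower frequency are retained: those who "do not stimulate the breast the recommended fourteen times a week, we will still consider them as completers of the study". Women who no longer wish to continue are handled differently: "If participants do not want to perform stimulation anymore, we consider this as a withdrawal of consent".

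SAP section 2.3 defines the modified ITT population by "considering only the participants who started the antenatal stimulation and/or participated in the breastfeeding consultation", and adds: "Participants who drop out before the breastfeeding consultation for any reason will not be included in any of our analyses". The per-protocol set is everyone who completed the questionnaires to 8 weeks after birth, whatever their compliance. Both sets apply to the secondary outcomes. Section 4.5 rules out imputation.

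The adherence outcome in section 4.2.2 is "Number of weekly expressions in the intervention group, measured through weekly push messages", summarised as median and IQR. No starting or continuation rate is a named outcome. The protocol's condition for moving to the larger trial (Sample Size) refers only to preterm birth.

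**The concern.** Stopping is one of the main ways an intervention like this can prove infeasible. The protocol's Background itself reports discomfort, pain and the burden on time and energy among women's negative experiences. Under section 2.2 a woman who stops becomes a withdrawal, and under section 4.5 nothing stands in for her later weeks. The weekly-expression summary then describes how often women expressed while they were still expressing, and says almost nothing about how many gave up. The pilot could finish with a respectable median and no planned statement of what share of the women asked to express from 34 weeks did so until birth.

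**Working it through.** **1. The route through the SAP for a woman in group A who expresses for two weeks and then stops.**
- Section 2.2: treated as having withdrawn consent.
- Section 2.3, modified ITT: she started, so she belongs to the population. Only dropouts before the consultation are removed from all analyses.
- Section 2.3, per-protocol: requires questionnaires to 8 weeks after birth, so a woman treated as withdrawn would not qualify.
- Section 4.5: no imputation, so the weeks after stopping have no value.
- Section 4.2.2: the median uses whatever weeks exist.

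Neither 2.2 nor 2.3 says whether her two reported weeks are kept or whether she is still followed to birth and beyond. The two sections must be reconciled.

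**2. Reference frequency.** The protocol's Intervention section gives two sessions a day: 2 × 7 = 14 a week, which agrees with SAP 2.2. The plan gives no expected adherence or stopping rate to reproduce.

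**3. How far the planned median responds to stopping.** From the protocol: 30 women in group A and 14 sessions a week. Assumed, not in the documents: 6 antenatal weeks (34+0 to 40+0); weekly count Binomial(14, p) while expressing, with p = 0.75 (range 0.60 to 0.90); each stopper stops after week 1, 2 or 3 with equal probability and expresses as often as the others until then. Medians are taken over all woman-weeks and averaged over 2,000 simulated trials, hence the decimals.

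| Stop (of 30) | Median, stoppers removed | Median, available weeks | Median, later weeks = 0 | Mean, available weeks | Mean, later weeks = 0 |
|---|---|---|---|---|---|
| 0 | 10.7 | 10.7 | 10.7 | 10.5 | 10.5 |
| 3 | 10.7 | 10.7 | 10.3 | 10.5 | 9.8 |
| 9 | 10.7 | 10.7 | 10.0 | 10.5 | 8.4 |
| 15 | 10.7 | 10.7 | 9.4 | 10.5 | 7.0 |

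The means can be checked by hand. While expressing, the mean is 14 × 0.75 = 10.5. Stoppers contribute 2 weeks on average. With 9 stopping, woman-weeks of expression are 21 × 6 + 9 × 2 = 144 out of 30 × 6 = 180, so counting zeros gives 10.5 × 144/180 = 8.4. With 15 stopping: 15 × 6 + 15 × 2 = 120, and 10.5 × 120/180 = 7.0.

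Across p = 0.60 to 0.90 and 3 to 15 stoppers, counting zeros lowers the median by about 0.1 to 1.3 and the mean by about 0.6 to 4.2.

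**4. Proportion still expressing, exact (Clopper-Pearson) 95% CI.**
- 27/30 = 90% (73 to 98)
- 21/30 = 70% (51 to 85)
- 15/30 = 50% (31 to 69)

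This measure separates the scenarios. The available-weeks median does not.

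**The case against.** The strongest reply is that section 2.3 keeps every woman who started, so stoppers are not lost. That is correct as far as it goes. A reader might infer that the SAP excludes stoppers altogether, but it does not say so. Weeks reported before stopping may count, and only the later weeks are clearly missing. Being in the population does not supply those weeks, however, and the table shows the same median whether stoppers are removed or contribute their early weeks.

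A reader might also infer that the count of women able to obtain milk before birth is limited to those who carried on. The text does not support this: it reads as an ever/never outcome, so a woman who obtained milk and then stopped can still count.

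Nor can one say that the pilot must report high adherence however many women stop. Low-frequency continuers are retained and would lower the median. Section 3.4 registers reasons for withdrawal, including side effects and time. Section 4.1 lists a weekly yes/no item on expression, and section 4.2.2 plans a bar plot per woman. A stopping rate could be derived from these. What stands is that the SAP does not commit to reporting one.

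Finally, a large effect can be made to appear by quoting a mean and giving stoppers zero for every week. The SAP reports a median, and women who stop have usually expressed for a while. On that footing the shift from counting zeros is modest: 0.7 with 9 of 30 stopping. Zeros alone are therefore a weak remedy.

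**Conclusion.** The point holds in a limited form and should be acted on. SAP 2.2 merges stopping the intervention with withdrawing consent, and with no imputation the only named adherence outcome is nearly insensitive to stopping: 10.7 sessions a week whether 0 or 15 of 30 women stop, under the assumptions above. Those assumptions on frequency, timing and number of weeks are illustrative. If stoppers expressed less often than others before stopping, the available-weeks median would respond somewhat. The structural conclusion does not depend on the values chosen: weeks after stopping have no value, stoppers leave the per-protocol set, and sections 2.2 and 2.3 leave their earlier data and further follow-up undefined. One of the two stated aims therefore lacks a planned measure of continuation. The absence of a numerical feasibility threshold for proceeding is a design preference rather than an error.

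**What to change.** In SAP 2.2, record stopping aBME as discontinuation of the intervention, separate from withdrawal of consent. Keep these women in follow-up and in the ITT analyses unless they also withdraw consent, and align section 2.3 with this. Count zero sessions from stopping until birth.

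In SAP 4.2.2, add for all women allocated to group A the number and proportion who started, were still expressing at 36+0, and were still expressing at birth. Give each an exact 95% CI, with the reasons for stopping from section 3.4. State how women who give birth before 36+0 enter the second proportion. The continuation proportion is the main remedy, and the zeros support it.

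The sponsor may also consider using the continuation proportion in the decision to proceed, but this is optional.

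The cost is mostly SAP wording. The weekly messages must continue after a woman stops expressing, and the documents do not say whether they do at present. The adherence figures will look less favourable.
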